SECTION 3: SUBJECT POPULATION(S) (INDIVIDUALS/RECORDS/SPECIMENS)**A. Subjects To Be Enrolled on this UCI protocol (Persons/Records/Biospecimens)**

1. Complete the table of subject enrollments below. *Include additional rows for subject category/group, as needed.*
2. If the study involves the use of existing records or biological specimens, specify the maximum number to be reviewed/collected and the number needed to address the research question.

Category/Group (e.g., adults, controls, parents, children)	Age Range (e.g., 7-12, 13-17, adults)	Maximum Number to be Consented or Reviewed/Collected (include withdrawals and screen failures)	Number Expected to Complete the Study or Needed to Address the Research Question
Children/Adolescents	8-17	35	26
Total: 35			

B. Overall Study Sample Size

If this is a multi-site study, provide the total number of subjects to be enrolled from all sites.

Not applicable: This study will only take place at UCI, and does not involve other sites.

Total number of subjects across all sites: <Type here>

C. Eligibility Criteria

1. Identify the criteria for inclusion and exclusion.

Patients will provide at least 28-day baseline data in the form a daily diary and must have at least 15 days of reported headache during this period, with at least 4 distinct episodes lasting at least 4 hours each.

Inclusion Criteria

- Children aged 8-17
- Medical history of chronic migraine for at least 6 months
- 15 or more headache days during a 4 week period

Exclusion criteria

- Previous use of any botulinum toxin of any serotype for any reason
- Diagnosis of Myasthenia gravis, Eaton-Lambert Syndrome, Amyotrophic Lateral Sclerosis
- Treatment of headache using acupuncture, transcutaneous electrical stimulation (TENS), cranial traction, dental splints, or injection of anesthetics/steroids within 4 weeks prior to the week -4 screening visit
- Pregnancy
- Hypersensitivity to any botulinum toxin preparation or to any of the components in the formulation and Infection at the proposed injection site" or added as "applicable contraindications to Botox

2. If eligibility is based on age, gender, pregnancy/childbearing potential, social/ethnic group, or language spoken (e.g., English Speakers only), provide a scientific rationale.

Not applicable: Subject eligibility is not based on these factors.

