- Block medications: medications and dosage used for the Botox ® injections
- Disposition: notes regarding patient's state during procedure

[figure not shown]
C. Research Procedures

1. Provide a detailed chronological description of all research procedures.

Methods

Given the existing evidence of efficacy in the available scientific data (adult and retrospective pediatric) and the PI's extensive personal experience in the pediatric population (where use of the study drug has

been found to be transformative), prolonged withholding of OnabotulinumtoxinA for the purpose of study was not considered reasonable by the PI. Thus, a study design minimizing the placebo control period while still allowing for comparison of OnabotulinumtoxinA to a control group, was desirable. An AB|BA cross-over design (which uses each patient has his/her own control, both minimizing recruitment numbers and the need for a control group which never receives treatment with OnabotulinumtoxinA), was selected as the best option after consultation. The influence of confounding covariates is reduced because each crossover patient serves as his or her own control. A four week baseline prior to treatment will act as a no-treatment control to compare to both the treatment and placebo. The study does not exclude patients on preventive or abortive migraine medication, in an attempt to demonstrate superiority on study drug over conservative medical management.

Diagrams 1-4: Recommended Injection Sites (A through G) for Chronic Migraine

(From BOTOX® Prescribing Information) Total of 31 Sites with a **maximum dose will be 155 U**

All data collection will follow Good Clinical Practices and HIPPA. This study has been submitted to the Institutional Review Board. Parent/guardian and/or child will sign an informed consent and assent (child) approving enrollment in study.

Patient Population

Children aged 8 – 17 years of age with a history of migraine meeting the criteria established in ICHD-II (2004), Section 1. Patients will provide at least 28-days (4 week) baseline data in the form a daily diary and must have at least 15 days of reported headache during this period, with at least 4 distinct episodes lasting at least 4 hours each. (Patients with continuous headache will thus be excluded as this may represent non-migraine symptoms). A total of 26 patients will be enrolled.

Data Collection

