Our primary endpoint will be the same as that used in the PREEMPT trial which examined the efficacy of OnabotulinumtoxinA in adult patients [1, 2]. Specifically, we will look for a reduction in frequency of headache days per month, as well as decrease in intensity utilizing a 10 point NRS scale (VAS when appropriate). In that trial, at baseline, patients reported 19.9 ± 3.6 headache days per month. The treatment group showed a reduction of 8.4 days, and the placebo group a reduction of 6.6 days (standard deviations on these reductions were not reported). Interpretation of the data was complicated by the medication regimens the patients were on at baseline (which frequently included over-use of opioid medications).

2. Describe the primary statistical method(s) that will be used to analyze the primary outcome(s) or endpoints.

Design considerations: Given the evidence of efficacy in the available scientific data and the PI's extensive personal experience in the pediatric population (where it has been found to be life-changing), prolonged withholding of OnabotulinumtoxinA for the purpose of study was not considered reasonable by the PI. Thus, a study design minimizing the placebo control period while still allowing for comparison of OnabotulinumtoxinA to a control group was desirable. An AB|BA cross-over design (which uses each patient has his/her own control, both minimizing recruitment numbers and the need for a control group which never receives treatment with OnabotulinumtoxinA), was selected as the best option. A four week baseline prior to treatment will act as a no-treatment control to compare to both the treatment and placebo.

The primary outcome will be the difference between treatment and placebo injections on headache frequency. The difference will be calculated as

$$(A_A - A_B) - \frac{1}{2} (A_A - A_B)$$

Where λ represents possible carry-over effects from the previous treatment period. Because the cross-over period is uniform and balanced, we will assume that period effects and sequence effects are aliased out. The treatment and placebo effects will be calculated as:

$$\hat{\mu}_A = \frac{1}{2}(\bar{Y}_{AB,1} + \bar{Y}_{BA,2}) \text{ and } \hat{\mu}_B = \frac{1}{2}(\bar{Y}_{AB,2} + \bar{Y}_{BA,1})$$

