Where \bar{Y}_{AB} represents the group mean of the respective cross over group periods. Given the adult baseline of 19.9 ± 3.6 headache days per month, the treatment reducing this to 6.6 days and the placebo to 8.4 days and assuming a concomitant reduction in SD since these numbers were not reported in the source manuscript, we find that the effect size for this difference (8.4 vs 6.6 with SD 1.35 for both groups) is 0.554, a Cohen's d of 1.33. A power analysis using a significance level of 0.05 and a power of 0.9 shows that 13 subjects per group will be needed for this study, or a total of 26 subjects (13 per group) if comparison were to be made by direct groupwise testing.

3. Describe the secondary statistical method(s) that will be used to analyze the secondary outcome(s) or endpoints.	N/A
4. If appropriate describe secondary or post hoc analyses of primary outcome(s) or other exploratory analysis.	N/A
5. Sample Size Determination: Explain how the overall target sample size was determined (e.g., power analysis; precision estimation), providing justification of the effect size for the primary outcome based on preliminary data, current knowledge/literature and/or cost consideration; if appropriate, provide sample size justification for secondary outcomes. Power analysis should (at least) match the primary outcome/endpoint.	

Given the adult baseline of 19.9 ± 3.6 headache days per month, the treatment reducing this to 6.6 days and the placebo to 8.4 days and assuming a concomitant reduction in SD since these numbers were not reported in the manuscript, we find that the effect size for this difference (8.4 vs 6.6 with SD 1.35 for both groups) is 0.554, a Cohen's d of 1.33. A power analysis using a significance level of 0.05 and a power of 0.9 shows that 13 subjects per group will be needed for this study, or a total of 26.

SECTION 7: RISK ASSESSMENT AND POSSIBLE BENEFITS

A. Risk Assessment

1. Indicate the appropriate level of review of this study, based upon your risk assessment.
 This study involves greater than minimal risk to subjects and requires Full Committee review. Skip to Section 7.B.
 This study involves no more than minimal risk and qualifies as Expedited research .
2. If this study involves no more than minimal risk, provide justification for the level of review and for all applicable Expedited Categories you have chosen.

B. Risks and Discomforts

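### The primary contrast uses four sequence-by-period means with no within-child model or analysis set, so if children leave after period 1 the result depends on an unstated choice

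*Combined protocol and SAP*

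**What the plan says.** Section 6.I, item 2, defines the target: "The primary outcome will be the difference between treatment and placebo injections on headache frequency". The formulas follow under "The treatment and placebo effects will be calculated as". The active effect is half the sum of the AB period-1 and BA period-2 means, and the placebo effect is half the sum of the AB period-2 and BA period-1 means. Each term "represents the group mean of the respective cross over group periods". On nuisance effects the section says: "Because the cross-over period is uniform and balanced, we will assume that period effects and sequence effects are aliased out".

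No paired test, within-child model, analysis set or rule for missing periods appears there. Items 3 and 4 of the same section, on secondary and exploratory analyses, are marked not applicable, so there is no sensitivity analysis either. The sample size is framed for "if comparison were to be made by direct groupwise testing".

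The design rationale in Section 6.C.1 is within-child: "The influence of confounding covariates is reduced because each crossover patient serves as his or her own control". The enrolment table in Section 3.A sets 35 against the column "Maximum Number to be Consented or Reviewed/Collected (include withdrawals and screen failures)" and 26 as the number expected to complete or needed. Section 6.C.1 says that 26 will be enrolled. No rate of dropout after randomisation is given.

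**The concern.** A crossover draws its strength from comparing each child with himself or herself. The formula does this automatically only when every child supplies both periods. Once some children supply period 1 alone, an analyst must decide whether those observations enter the period-1 means. The plan does not decide. The two choices differ in precision, and when dropout is related to response they err in opposite directions. In a trial of 26 children a choice of this kind should not be left until the data have been seen.

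**Working it through.** **The plan's own figure.** The inputs in Section 6.I are 8.4 against 6.6 days with SD 1.35, so d = 1.8/1.35 = 1.33. The stated 0.554 is 1.33/√(1.33² + 4). A two-sided, two-sample t-test at 0.05 and 90% power needs 12.92, hence 13 per group (power 90.2%). The figure reproduces, but as an unpaired calculation. It says nothing about how the crossover contrast will be tested, and this point does not change it.

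**The estimator.** Write D for active minus placebo; negative means fewer headache days on active treatment:

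D = ½[(AB₁ − AB₂) + (BA₂ − BA₁)]

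With complete data each bracket is a mean of within-child differences, so pairing is intact. With 13 per sequence, Var(D) = σ²(1 − ρ)/13. At an assumed SD of 5 and correlation ρ of 0.7 this is 25 × 0.3/13 = 0.577, an SE of 0.76.

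**Precision under random dropout.** As an upper bound take 1 − 26/35 = 25.7% leaving after period 1 (the 35 also covers screen failures). Then n₂ = 13 × 26/35 = 9.66.
- All available: ½σ²(1/13 + 1/9.66 − 2ρ/13) = 12.5 × (0.0769 + 0.1035 − 0.1077) = 0.909, SE 0.95. Simulation, where the number leaving varies, gives 0.98.
- Completers: σ²(1 − ρ)/9.66 = 7.5/9.66 = 0.776, SE 0.88.
- Mixed model, simulated: SE 0.87–0.88, so the variance ratio for all-available means is (0.98/0.87)² = 1.27.

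The two hand formulas coincide at ρ = 0.5, and below that the all-available means are the more precise. Over ρ of 0.5–0.7 the all-available variance is about 10–30% above the mixed model's.

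**Bias when dropout depends on the period-1 count.** Let c be the shift in a sequence's period-1 mean when only the stayers are kept. With normal data their period-2 mean shifts by ρc. Then:
- All available: bias = ½ρ(c_BA − c_AB)
- Completers: bias = −½(1 − ρ)(c_BA − c_AB)

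The signs are opposite, and both vanish when selection is the same in the two sequences. With a common dropout mechanism and no treatment effect, c_BA = c_AB and the bias is zero.

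Large-sample simulation agrees. Inputs: true difference −1.80, the documents' baseline SD of 3.6, period means 19.9 − 8.4 = 11.5 and 19.9 − 6.6 = 13.3, and 25.7% dropout overall.

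| Dropout rule | ρ | All available | Completers | Likelihood model |
|---|---|---|---|---|
| Graded (AB 22%, BA 30%) | 0.3 | −1.84 | −1.72 | −1.80 |
| | 0.5 | −1.86 | −1.75 | −1.81 |
| | 0.7 | −1.88 | −1.76 | −1.80 |
| Worst quarter leave (AB 18%, BA 34%) | 0.3 | −1.94 | −1.51 | −1.81 |
| | 0.5 | −2.01 | −1.59 | −1.80 |
| | 0.7 | −2.09 | −1.68 | −1.80 |

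Graded dropout gives 2–4% bias in either direction (0.038/1.80 to 0.076/1.80). If the worst quarter leave, all-available means exaggerate by up to 0.290/1.80 = 16%, and completers shrink the effect by up to 0.287/1.80 = 16%. As a check on the algebra, at ρ = 0.7 the biases are −0.290 and +0.123. Their ratio in size is 2.36, against 0.7/0.3 = 2.33.

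**At the trial's size.** Inputs: 13 per sequence, SD 5, and a 0.7 chance of leaving if the period-1 count exceeds 16, which gives about 17% dropout.
- ρ = 0.5: all available −1.91 (SE 1.17), mixed model −1.81 (1.07); variance ratio 1.20.
- ρ = 0.7: all available −1.95 (SE 0.98), mixed model −1.80 (0.82); variance ratio 1.43.
- Completers, in a separate run of the same setting: −1.71 (SE 1.04) and −1.73 (0.83), against mixed-model SEs of 1.04 and 0.84.
- SD 3.6 instead of 5: all-available bias 7–8%, variance ratio 1.17–1.40.
- No treatment effect, ρ = 0.7: bias about 0, but the all-available variance is still 46% larger.

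With the mixed model fitted by REML at SD 3.6 and 5, all-available means ranged from −1.87 to −1.96 (4–9% too large) and completers from −1.66 to −1.74 (3–8% too small). The mixed model stayed near −1.80.

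**The case against.** The strongest reply is that this is an omission and not a biased estimator. The formula is a valid within-child contrast with complete data, and the own-control language points naturally to children with both periods. On that reading an early leaver counts in neither mean, the precision loss largely disappears and the bias is conservative. This stands. A reader might infer that such a child must count in one treatment mean only and so flatter active treatment, but the documents do not say which children enter each mean.

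Nor is the self-control rationale lost. At SD 5 and ρ = 0.7 the SE is 0.76 with complete data and about 1.0 on the all-available reading. A parallel comparison of 13 against 13 would give 5 × √(2/13) = 1.96. Most of the crossover gain survives.

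It is also tempting to say that children doing badly on saline are the most likely to leave. The documents contain no such statement. Every child receives active treatment in the last two blocks (Section 6.B.1), which is a reason to stay, and AB children who respond poorly may leave too. Only the difference in selection between sequences produces bias.

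Finally, the evidence of expected withdrawals is a form column that also counts screen failures, so the dropout rate is unknown. That limits what can be said about size, but it does not supply the missing rule.

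**Conclusion.** The point holds as a gap in the primary analysis. The plan gives a four-mean formula and no within-child model or analysis set, and under dropout the answer depends on which children are averaged. Under response-dependent dropout, all-available means carry about 15–45% more variance than a mixed model and overstate benefit by about 2–9% in most scenarios. Completers-only means understate it by about 3–8% in the threshold scenarios. The extreme case is about 16% in either direction.

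The bias is small beside an SE of roughly 0.8–1.2 days at SD 5. It needs both a real treatment effect and dropout that follows response, and it would not on average create an effect where none exists. SD (3.6 or 5), correlation (0.3–0.7 for bias, 0.5–0.7 for precision) and dropout (10% to 25.7%) are assumptions, since the documents give no correlation and no dropout rate. The change is worth making because it is cheap and removes a choice that could otherwise be made after the data are seen.

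**What to change.** In Section 6.I, item 2, replace the four-mean formula as the analysis method with a linear mixed model on headache days per month, the plan's own unit:
- fixed effects for treatment and period, and a random effect for child;
- REML with a small-sample degrees-of-freedom correction;
- all randomised children with at least one treatment block observed;
- the treatment coefficient with its 95% confidence interval as the primary result.

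State that the carry-over term shown in that section is assumed to be zero in this model. Give the within-child difference in children completing both periods as a sensitivity analysis.

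The cost is plan wording and a few lines of code. No new data are needed and the sample size does not change. With complete data the estimate is the same as the formula's. The downside is that the model assumes dropout depends only on observed data; a sensitivity analysis allowing dropout to depend on unobserved values could be added.

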OnabotulinumtoxinA

Botulinum neurotoxin-A is a purified neurotoxin complex produced by the anaerobic bacterium *Clostridium botulinum*. [11,12]. The main mechanism of action of botulinum toxin involved the targeting of the neuromuscular junctions by means of a specific cleavage of the soluble N-ethylmaleimide-sensitive factor (NSF)-attachment protein receptor complex (SNARE)-like synaptosomal-associated protein of 25kDa (SNAP-25) [11, 12]. The final outcome of this multi-step process is the inhibition of pain neurotransmission (i.e. Chemo denervation), including the inhibition of the release of migraine-related neuropeptides (eg CGRP and SP) and glutamate. [11,12,13]

OnabotulinumtoxinA was approved by the FDA in 2010 for adult patients with common migraine, with the indication of >15 headache days per month, with headache lasting 4 or more hours each day in people 18 years or older. BOTOX® prevents up to 9 headache days a month (versus up to 7 in placebo) and is injected every 3 months. [14,15]

While randomized, double blind, placebo-controlled trials evaluating OnabotulinumtoxinA efficacy in migraine prophylaxis in adult literature demonstrates statistically significant results towards safety and efficacy [14, 15], no such randomized, double blind placebo controlled data for safety or efficacy exists

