Our primary endpoint will be the same as that used in the PREEMPT trials which examined the efficacy of OnabotulinumtoxinA in adult patients aged 18 or greater [14, 15]. Specifically, we will look for a reduction in frequency of headache days per month. In that trial, at baseline, patients reported 19.9 ± 3.6 headache days per month. The treatment group showed a reduction of 8.4 days, and the placebo group a reduction of 6.6 days (standard deviations on these reductions were not reported). Interpretation of the data was complicated by the varied medication regimens the patients were on at baseline (which frequently included over-use of opioid medications).

In 1999 the Migraine Disability Score (MIDAS) was developed by Stewart et al. [10] which is an easy-to use 5 item questionnaire accepted as a means to diagnose and follow adult headache. Hershey et al developed the pediMIDAS based on MIDAS but utilizes 6 questions, 3 addressing school attendance and functioning, and 3 evaluating participation in events outside of school. [22]. The questionnaire is based on the patient's recall of previous 3 months and can be used longitudinally to assess response. [1] In the clinical setting, the PedMIDAS can be helpful in assessing a patient's migraine burden and response to therapy. Some researchers advocate its use as an outcome measure in clinical trials. The Pediatric Migraine Disability Assessment (PedMIDAS) is the only validated clinical tool available to estimate migraine disability in the school-aged child, aged 4-18. [22]

Each data point will be collected at baseline, 6 weeks, 12 weeks, 18 weeks, 24 weeks, 30 weeks, 36 weeks, 42 weeks, and 48 weeks

2. Describe the duration of a subject's participation in the study. If there are sub-studies, include duration of participation in each sub-study.

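### The sample size treats the reference trial's reductions (8.4 and 6.6 days) as levels reached, so SD 1.35, d = 1.33 and the stated 90% power are unsupported

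*Combined protocol and SAP*

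**What the plan says.** The reference-trial result is given in two incompatible forms.

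- **As reductions.** Section 6.C (Data Collection) and Section 6.I, item 1, both say: "The treatment group showed a reduction of 8.4 days, and the placebo group a reduction of 6.6 days". Both add that no SDs were reported for these reductions. The background on the drug in Section 1 is also on the change scale: up to 9 days prevented against up to 7 on placebo.
- **As levels reached.** Section 6.I, items 2 and 5, start from the baseline ("Given the adult baseline of 19.9 ± 3.6 headache days per month") and continue with "the treatment reducing this to 6.6 days and the placebo to 8.4 days".

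Item 2 then obtains an SD by "assuming a concomitant reduction in SD since these numbers were not reported in the source manuscript"; item 5 does the same in nearly the same words. Both arrive at SD 1.35 in each group, an effect size of 0.554, Cohen's d of 1.33 and, for 90% power at the 0.05 level, "13 subjects per group will be needed for this study, or a total of 26". Item 2 qualifies that number with "if comparison were to be made by direct groupwise testing". Item 5, the formal sample-size statement, has no such qualifier. The planned comparison is an AB|BA crossover with each patient as his or her own control.

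**The concern.** A reduction of 8.4 days has become a level of 8.4 days, and likewise for 6.6, with the two figures changing arms. Both readings cannot be true of one trial. The direction and the 1.8-day gap are the same either way, so the slip is easy to miss. It matters because the plan shrinks the SD along with the mean: if the means are wrong, the shrunken SD is wrong too, and d = 1.33 and the 90% follow from it.

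This calculation is the only justification for 26 patients. A null result read against a claimed 90% power would look like evidence of no effect, when the real power could be far lower. If the power is in fact adequate, the plan does not show that either.

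**Working it through.** **Inputs from the documents.** Baseline 19.9, SD 3.6; reductions 8.4 (treatment) and 6.6 (placebo); SD 1.35; alpha 0.05; power 0.90; 13 per group. **Assumed here, because the documents do not say:** a two-sided test, equal SDs in both conditions, 19.9 as the baseline of both arms, no carry-over, and the on-treatment SDs and within-patient correlations (rho) shown below.

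**1. Reproducing the plan's figure.** d = (8.4 − 6.6)/1.35 = 1.8/1.35 = 1.33. The 0.554 is d expressed as a correlation: d/√(d² + 4) = 1.33/√(1.33² + 4) = 0.554. A two-sided two-sample t-test with 13 per group has power 90.3%. The stated number therefore follows from its inputs; the inputs are the problem.

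**2. Levels implied by the reported reductions.** Treatment: 19.9 − 8.4 = 11.5. Placebo: 19.9 − 6.6 = 13.3. The difference is still 1.8.

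**3. The SD.** The plan gives no formula. Scaling the baseline SD to the average misread level, (6.6 + 8.4)/2 = 7.5, gives 3.6 × 7.5/19.9 = 1.36, close to 1.35. That this is where 1.35 came from is an inference. The same rule on the average implied level, (11.5 + 13.3)/2 = 12.4, gives 3.6 × 12.4/19.9 = 2.24.

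**4. The plan's own groupwise basis, difference 1.8.**

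| SD | d | Power, 13 per group | Per group for 90% |
|---|---|---|---|
| 1.35 | 1.33 | 90% | 13 |
| 2.24 | 0.80 | 50% | 34 |
| 3.6 | 0.50 | 23% | 86 |

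**5. The AB|BA comparison.** The SD of the within-patient difference is SD × √(2(1 − rho)). Power is from the noncentral t with noncentrality 1.8 × √26 / (SD of difference) and 24 df, i.e. a period-adjusted test in 26 completers. Completers needed are rounded up to an even number for two equal sequences.

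| SD | rho | SD of difference | Power, N = 26 | Completers for 90% |
|---|---|---|---|---|
| 2.24 | 0 | 3.17 | 79% | 36 |
| 2.24 | 0.3 | 2.65 | 91% | 26 |
| 2.24 | 0.5 | 2.24 | 98% | 20 |
| 2.24 | 0.7 | 1.74 | over 99% | 14 |
| 3.6 | 0 | 5.09 | 41% | 88 |
| 3.6 | 0.3 | 4.26 | 54% | 62 |
| 3.6 | 0.5 | 3.60 | 69% | 46 |
| 3.6 | 0.7 | 2.79 | 88% | 28 |

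Using a plain paired t-test (25 df) instead changes the power by less than 0.002.

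**6. What 90% requires.** With 26 completers the SD of the within-patient difference must be at most 2.72 days. Solving rho = 1 − 2.716²/(2 × SD²) gives rho of at least 0.27 for SD 2.24 and at least 0.72 for SD 3.6.

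**The case against.** The strongest reply is that the crossover rescues the design. It was chosen because patients act as their own controls, so positive correlation is its premise. With SD 2.24, 90% is reached once the correlation is about 0.27. On that view item 2's groupwise figure was a conservative ceiling, and the groupwise shortfalls in step 4 do not describe this trial. Part of this stands: the misreading does not prove the trial underpowered, and step 4 shows only how far the plan's own calculation moves. But the groupwise figure is conservative only if SD 1.35 holds, and the plan gives no within-patient SD or correlation from which the rescue could be shown.

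A second reply is that the origin of 1.35 is inferred, and the scaling gives 1.36 rather than 1.35. That is correct. The finding does not depend on it: the plan ties 1.35 explicitly to 8.4 versus 6.6 as levels and offers no other support.

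A third is that 2.24 comes from the same unsupported scaling rule, and that 3.6 is a baseline SD rather than an upper bound. Both points are fair. With an assumed SD of 5, power in 26 completers would be 42% at correlation 0.5 and 62% at 0.7. This widens the range of possible power and does not restore the 90% claim.

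Finally, all crossover figures assume 26 completers. The enrolment table in Section 3.A supports that (35 consented, 26 completing), but Section 6.C (Patient Population) gives 26 as the number enrolled. On that reading any dropout lowers the power.

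**Conclusion.** The concern holds. The sample-size statements contradict the reference figures reported elsewhere in the same document, and SD 1.35, effect size 0.554, d = 1.33 and the 90% power have no valid basis as written. The 1.8-day difference is unaffected. The power of the actual design is unknown: with 26 completers it runs from 41% to over 99% across SDs of 2.24 to 3.6 and correlations of 0 to 0.7. Those ranges rest on the assumptions listed in the check. The contradiction itself rests on none of them. It must be fixed because it concerns the primary endpoint and the only justification for the trial's size.

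**What to change.** In Section 6.I, items 2 and 5:

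- Correct the levels to 11.5 (treatment) and 13.3 (placebo), or give the figures as reductions of 8.4 and 6.6.
- Delete SD 1.35, 0.554 and d = 1.33.
- Replace the 90% claim with a conditional statement for the crossover, for example: *The expected difference is 1.8 days. The on-treatment SD and within-patient correlation are not known. With 26 completers and a period-adjusted within-patient test (two-sided 0.05, no carry-over), power at correlation 0, 0.3, 0.5 and 0.7 is 79%, 91%, 98% and over 99% if the SD is 2.24, and 41%, 54%, 69% and 88% if it is 3.6.*
- State which SD and correlation the sponsor considers realistic, and why. Equivalently, justify an SD of the within-patient difference against the 2.72-day limit.

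The test named in the example should match whatever primary analysis is finally specified; item 2 names no test and carries a carry-over term.

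The correction is wording in two places. Its cost is a power statement that is less favourable and openly conditional. If the sponsor considers an SD near 3.6 with a correlation of 0.5 or below realistic, 26 completers fall short of 90% (46 are needed at 0.5). The sponsor must then either accept the lower power openly or reconsider the number.
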